7.10.1.6. Subgroup Analyses

Subgroup analyses are described in section 7.9.

7.10.2. Primary Effectiveness

The primary effectiveness objective compares the rate of chronic treatment success between study arms.

7.10.2.1. Hypothesis

The primary effectiveness objective will be assessed with the following hypothesis:

$$H_0: h_{Control}(t) = h_{Treatment}(t) \text{ for all } t \leq T \text{ years}$$

$$H_A: h_{Control}(t) \neq h_{Treatment}(t) \text{ for some } t \leq T \text{ years}$$

where $h(t)$ is the hazard function (risk) of chronic treatment failure at time t and T is the total study time. Hazard functions and survival functions are transformations of each other.

7.10.2.2. Performance Criteria and Rationale

If the hazard ratio for chronic treatment failure between the Treatment and Control only arms is less than one and the two-sided log-rank p-value is less than 0.05, it will be concluded that the pulmonary vein isolation and renal artery denervation procedure results in a higher rate of chronic treatment success.

Given the feasibility nature of this study and relatively small sample size (n=70 for the final analysis), even if the pulmonary vein isolation and renal artery denervation procedure results in a clinically meaningful improvement in the rate of chronic treatment success (e.g. an absolute 10-15% higher chronic treatment success rate through 6 months), the log-rank test may not reach statistical significance ($p<0.05$).

This study is intended to provide data to support the design of a pivotal trial. The estimates of the chronic treatment success rate for each study arm can provide that data whether the log-rank test is statistically significant or not.

Rationale for the performance criteria can be found in section 12.4.3 of the CIP.

7.10.2.3. Endpoint Definition

The endpoint for this objective is chronic treatment success. Chronic treatment success is freedom from chronic treatment failure. Therefore, comparing the rate of chronic treatment success is equivalent to comparing the risk of chronic treatment failure.

Chronic treatment failure is defined as the occurrence of either

- 1) a documented episode of AF recorded on Reveal LINQ
- 2) an intervention for AF

occurring after a blanked follow-up period of 90 days from the study treatment procedure. AF episodes and repeat ablations that occur within 90 days of the study treatment procedure will not constitute chronic treatment failure.

Intervention for AF is defined as an invasive procedure intended for the definitive treatment of AF, including any ablation of the pulmonary veins or atrial triggers (other than protocol-specified ablation), interruption of AV nodal function, procedures to alter left atrial conduction or function such as the Maze procedure, or the implantation of an atrial pacemaker or atrial defibrillator; whether approved by relevant regulatory authorities or not for such indications; excluding electrical or pharmacologic cardioversion of arrhythmias and excluding procedures solely directed at the treatment of atrial flutter or atrial tachycardias.

7.10.2.4. Analysis Methods

A log-rank test will be used to perform this hypothesis test. The log-rank test uses the time that each subject is free from chronic treatment failure, defined from the date of procedure to the date of chronic treatment failure, if it occurs, or latest of the following: a) the last follow-up visit date, or b) the last date on which AF was assessed, if chronic treatment failure does not occur during the subject's study follow-up. Subjects will be included through all available study follow-up.

In addition to the log-rank test, Kaplan-Meier curves will be used to estimate the rate of chronic treatment success. Cox proportional hazards regression will be used to estimate the hazard ratio and its 95% confidence interval between study arms.

Code similar to the following can be used for the log-rank test and Kaplan-Meier curves:

```
ODS graphics on ;
PROC LIFETEST DATA=survData conftype=loglog;
    Plots = (survival(atrisk = 0 to <end time> by <interval time>)) ;
    STRATA trtGroup;
    TIME time*event(0);
    TEST trtGroup;
RUN;
ODS graphics off ;
```

Code similar to the following can be used for the Cox proportional hazards model:

```
PROC PHREG DATA = survData;
    CLASS trtGroup;
    MODEL time*event(0) = trtGroup / TIES = efron;
RUN;
```

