#### **12.4.2 Performance Requirements**

If the hazard ratio for chronic treatment failure between the Treatment and Control only arms is less than one and the two-sided log-rank p-value is less than 0.05, it will be concluded that the pulmonary vein isolation and renal artery denervation procedure results in a higher rate of chronic treatment success.

Given the feasibility nature of this study and relatively small sample size, even if the pulmonary vein isolation and renal artery denervation procedure results in a clinically meaningful improvement in the rate of chronic treatment success (e.g. an absolute 10-15% higher chronic treatment success rate through 6 months), the log-rank test may not reach statistical significance ( $p < 0.05$ ).

This study is intended to provide data to support the design of a pivotal trial. The estimates of the chronic treatment success rate for each study arm can provide that data whether the log-rank test is statistically significant or not.

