#### **12.4.6 Sample Size**

There will be at least 78% power to test this objective provided at least 70 subjects undergo randomization.

The sample size calculation is based on the following assumptions:

- 1:1 randomization
- Constant randomization rate over 16 months
- Last enrolled subject followed through 6 months post-procedure
- 50% chronic treatment success in the PVI only arm versus 75% in the Treatment arm (equivalent to a hazard ratio of 0.415) through 6 months post-procedure
- Constant hazard ratio over all follow-up
- Cumulative alpha of 0.05. Any planned interim analyses will be constructed so that the overall Type I error of the study is no greater than 0.05.
- Constant attrition (dropout) of 5% per 6 months

The sample size calculation was performed in PASS 2008 using the log-rank (Lakatos) procedure. Accounting for a study attrition rate of up to 5% per 6 months ensures that the study will maintain the planned power of 78% in case attrition is higher than expected (approximately 1% per 6 months).

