5.1. Study Design Summary

The Symplicity AF study is a prospective, randomized, multi-center, investigational, feasibility, clinical study. The study is expected to be conducted at up to 12 centers located in The United States. Up to 245 subjects will be enrolled in the study to ensure there are 70 randomized subjects. The number of

enrollments permitted relative to the number of subjects to be randomized is high since it is expected that a fair number of subjects will not meet all screening criteria (rigorous blood pressure monitoring and renal anatomy) once consented. Center randomization will be capped at 30% (21) of the total randomized subjects.

Randomized study subjects will be followed for a minimum of six months, and then every six months thereafter until official study closure as determined by Medtronic and/or regulatory authority, whichever occurs first. Accordingly, the expected total study duration, if the study conducts a final analysis, is approximately fifty-seven months, representing approximately fifty-one months of enrollment and six months of subject follow-up after the last patient has undergone the study procedure. The figure below illustrates the study design.

Interim analyses of the primary effectiveness objective may take place and if data are deemed to sufficiently characterize this study objective by the sponsor at one of these analyses, enrollment may be stopped.

Figure 1. Study Design Flowchart

Two interim analyses are planned. The first analysis will be conducted after 32 subjects are randomized and have completed their six-month visit. If the primary effectiveness objective is not passed after this analysis, the second will be conducted after 50 patients have been randomized and have completed their six-month visit. If neither interim analysis results in a successful primary effectiveness objective, the final analysis will be conducted once 70 patients are randomized and have completed their six-month visit.

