The original sample size calculation was performed in PASS 2008 using the log-rank (Lakatos) procedure. Updates to incorporate interim analyses were performed using EaST, version 6.4.1 with the survival module. Accounting for a study attrition rate of up to 5% per 6 months ensures that the study will maintain the planned power of 78% in case attrition is higher than expected (approximately 1% per 6 months).

A summary of the EaST output detailing the analyses is given on the following page.

Design: Survival Endpoint: Two-Sample Test - Parallel Design - Logrank Given Accrual Duration and Study Duration

Test Parameters	
Design ID	Des3
Design Type	Superiority
Number of Looks	3
Test Type	2-Sided
Specified α	0.05
Power	0.786
Model Parameters	
HR = λ_c/λ_e	
Under H0	1
Under H1	0.415
Ratio of % Surv. at Period #1:	1.5
Cum. % Surv. by Time =	6
Control (S_c)	50
Treatment (S_e)	75
Var (Log HR)	Null
Allocation Ratio (n_e/n_c)	1
Boundary Parameters	
Spacing of Looks	Unequal
Efficacy Boundary	Interp.
Accrual / Dropouts Parameters	
Cum % Accrued	100
Accrual Duration	16
Max Study Duration	22
Dropout	Yes

Variable Follow-Up Design: All subjects are followed until failure, drop out or end of study.

Sample sizes and events have been rounded.

Sample Size Information

	Control Arm	Treatment Arm	Total
Sample Size (n)			
Maximum	34	35	69
Expected H1	31.666	31.666	63.331
Expected H0	34.288	34.288	68.577
Events (s)			
Maximum	25	16	41
Expected H1	22.52	13.022	34.031
Expected H0	20.325	20.325	40.62
Dropouts (d)			
Maximum	2	3	5
Expected H1	1.723	2.547	4.27
Expected H0	1.985	1.985	3.97
Maximum Information (I):			10.25

Accrual and Study Duration

	Accrual Duration	Study Duration
Maximum	16	21.998
Expected H1	14.686	19.024
Expected H0	15.902	17.361

Stopping Boundaries: Look by Look

Look #	Info. Fraction (s/s_max)	Events (s)	Cumulative α Spent	Boundaries
Efficacy Z				
Upper		Lower		
1	0.341	14	0.01	2.576 -2.576
2	0.463	19	0.015	2.611 -2.611
3	1	41	0.05	2.049 -2.049

Events, Sample Size, Dropouts, Pipeline and Analysis Times: Look by Look (Under H0)

Look #	Info. Fraction (s/s_max)	Sample Size (n)	Events (s)	Dropouts (d)	Pipeline (n-s-d)	Analysis Time	Boundary Crossing Prob (Incremental)
Efficacy							
Upper		Lower					
1	0.341	39	14	2	23	8.863	0.005
2	0.463	46	19	2	25	10.639	0.003
3	1	69	41	4	24	17.481	0.017

Events, Sample Size, Dropouts, Pipeline and Analysis Times: Look by Look (Under H1)

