7.8. Interim Analyses

Two interim analyses are planned for the study. These analyses would be performed after 32 and 50 subjects have been randomized and completed their 6-month follow-up visits, respectively. Both the

sponsor and the DMC will assess the results of the interim analyses of the primary effectiveness objective and based on this assessment, the sponsor may decide to stop enrollment. However, while there are formally defined stopping rules for a successful primary effectiveness endpoint, there are no stopping rules for futility.

Patients randomized to the trial who have not reached 6-months of follow-up are not considered in assessing the primary effectiveness objective.

The time points of the analyses and criteria for study success are given in Table 1 below:

Table 2: Timing and Success Criteria for Interim and Final analyses

Time Point of Interim Analyses of the Primary Effectiveness Objective	Cumulative Alpha	Boundary*	Pass/Fail Primary Effectiveness Objective
After 32 subjects were randomized and completed their 6-month visit	0.01	0.01	If a two-sided p-value ≤ 0.01 , in favor of the treatment group, then the study passed the primary effectiveness objective
After 50 subjects were randomized and completed their 6-month visit	0.015	0.008	If a two-sided p-value ≤ 0.008 , in favor of the treatment group, then the study passed the primary effectiveness objective
Final Analysis: After 70 subjects were randomized and completed their 6-month visit	0.05	0.04	If a two-sided p-value ≤ 0.04 , in favor of the treatment group, then the study passed the primary effectiveness objective

*Boundaries were calculated using EaST 6.4.1, using the Survival Module.

In addition to reviewing the effectiveness data from the interim analyses, the DMC will be responsible for assessing the accumulating data on safety of the procedures during the study. The primary responsibility of the DMC is to safeguard the interests of study participants. The DMC also monitors the overall conduct of the clinical study. Further information regarding the DMC is found in Appendix C: Data Monitoring Committee.

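### After an interim efficacy pass, the plan reports fixed-sample hazard ratios, intervals and success rates that on average overstate the effect, and it does not settle which data cut supplies them

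*SAP*

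**What the plan says.** SAP 5.1 and 7.8 set efficacy looks at 32 and 50 completers and a final analysis at 70: "The first analysis will be conducted after 32 subjects are randomized and have completed their six-month visit". The look-1 rule in SAP 7.8 is met "If a two-sided p-value ≤ 0.01 , in favor of the treatment group". SAP 5.1 schedules each later analysis only if the earlier one does not pass. SAP 7.8 leaves subjects who have not reached 6 months out of the assessment, and leaves stopping of enrolment to the sponsor.

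The EaST output in SAP Section 6 gives look number, information fraction, events, cumulative alpha and Z limits: "1 0.341 14 0.01 2.576 -2.576", "2 0.463 19 0.015 2.611 -2.611" and "3 1 41 0.05 2.049 -2.049".

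For estimation, SAP 7.10.2.4 and Protocol 12.4.4 specify Kaplan-Meier curves, and "Cox proportional hazards regression will be used to estimate the hazard ratio and its 95% confidence interval between study arms". Neither document gives an adjusted estimate, a sequential interval, or a caution about estimates after an early pass.

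On use, Protocol 12.4.2 says "This study is intended to provide data to support the design of a pivotal trial". That section and SAP 7.10.2.2 name the arm-level success rates as the estimates that can serve this. Protocol 12.1 has all objectives analysed once the last randomised subject completes the 6-month visit.

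**The concern.** The looks changed the p-value thresholds and left the estimates alone. A trial that passes early does so because the observed effect was large at that moment, so the ordinary estimate is, on average, too far from no effect, and its interval covers the truth too rarely. This matters more than usual here, because the stated purpose of the study is to supply estimates for a pivotal design, and an early pass is the outcome most likely to prompt one.

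At the final look there is a second, smaller mismatch. An ordinary 95% interval corresponds to p<0.05, while SAP 7.8 requires p≤0.04.

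**Working it through.** **Inputs.** From SAP Section 6: 14, 19 and 41 events; Z limits 2.576, 2.611 and 2.049; 1:1 allocation; design HR 0.415 (50% v 75% success at 6 months).

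**Model.** Information = events/4; Z has mean |ln HR| × √(events/4) and independent increments between looks; 4 million simulated trials.

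**The plan's own figures first.** At HR 0.415 the look-by-look passing probabilities are 17.6%, 10.1% and 50.9%, total 78.6%, as in SAP Table 1. Under no effect, cumulative two-sided alpha is 0.010, 0.015 and 0.050. The model therefore matches the SAP's design.

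**HR needed to pass** = exp(−2Z/√events):
- Look 1: 2 × 2.576/√14 = 1.377, giving 0.252
- Look 2: 2 × 2.611/√19 = 1.198, giving 0.302
- Final: 2 × 2.049/√41 = 0.640, giving 0.527

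Both interim limits are more extreme than the design HR of 0.415.

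**Estimates given an early pass (planning counts):**

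| True HR | P(early pass) | Geometric-mean HR | Ordinary 95% CI coverage |
|---|---|---|---|
| 0.415 | 27.7% | 0.21 | 91% (look 1: 86%) |
| 0.70 | 4.5% | 0.23 | about 20% (look 1: 11%) |

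A true HR of 0.70 means 0.50^0.70 = 62% v 50% success, inside the 10-15 point benefit that Protocol 12.4.2 calls clinically meaningful. The early-pass HR is about the same in both rows, so it says little about which is true. Over all outcomes at 0.415, the geometric mean is 0.37 and coverage 94.7%.

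**Sensitivity to the event count.** Look 1 is triggered by 32 completers, not by 14 events. Patient-level simulation gives about 16-18 events with the 16-month accrual of the design, and 20-24 with the 51 months now expected. The limit is then exp(−2 × 2.576/√16) = 0.28 to exp(−2 × 2.576/√24) = 0.35. At true HR 0.415 the median passing Cox HR is 0.19-0.25.

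**Arm success rates.** In the same simulation, mean 6-month Kaplan-Meier success after a look-1 pass is 83-85% v 39-42%, a difference of 41-45 points. The truth is 75% v 50%, a difference of 25 points.

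**Effect of full follow-up.** If everyone randomised by look 1 is followed to 6 months, the median HR after a look-1 pass is 0.26-0.29. That is closer to 0.415, but still short of it.

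**Interval at the look-1 boundary.** Ordinary 95%: exp(−1.377 ± 1.96 × 2/√14) = 0.089 to 0.719. Repeated interval with the look-1 limit: exp(−1.377 ± 2.576 × 2/√14) = 0.064 to 1.00. The bias-adjusted (Whitehead) HR for an observed 0.252 is about 0.29.

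**Look-2 boundary.** The stage-wise median-unbiased HR is 0.314 against 0.302, and the upper limit 0.80 against 0.74.

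**Final boundary.** Ordinary 95%: exp(−0.640 ± 1.96 × 2/√41) = 0.286 to 0.973. The stage-wise upper limit is 1.00, which agrees with the rule. In about 2% of trials the final p falls between 0.04 and 0.05: the ordinary interval excludes 1, yet the objective fails under SAP 7.8. (SAP 7.10.2.2 and Protocol 12.4.2 still state 0.05.)

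**The case against.** Several points on the other side are sound.

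- *Type I error is protected.* Protocol 12.4.6 promises that "Any planned interim analyses will be constructed so that the overall Type I error of the study is no greater than 0.05", and the EaST boundaries deliver it. The gap is in estimation only.
- *Overall performance is near nominal.* At HR 0.415 overall coverage is 94.7%, and the 20% coverage at HR 0.70 belongs to an outcome seen in 4.5% of trials. This stands; the problem is conditional on an early pass.
- *Full follow-up may already be intended.* Protocol 12.1 points that way. But SAP 5.1 makes the later analyses conditional on not passing, and SAP 7.8 excludes subjects short of 6 months. The documents do not say which cut supplies the reported figures.
- *The standard remedy does little where it is most wanted.* Under stage-wise ordering, a look-1 stop gives the same estimate and interval as a fixed design. Look 1 supplies 17.6 of the 27.7 points of early passes (64%). The method also assumes that stopping follows the boundary, while here it is at the sponsor's discretion.

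A reader might also infer that the pivotal trial would be sized on the inflated HR: 4(1.96 + 0.84)²/(ln HR)² gives 13 events at HR 0.21 against 41 at 0.415. The documents do not support that step, because the estimates they name are the arm success rates. Those rates carry the same bias, so the concern survives in that form.

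**Conclusion.** The point holds as a conditional one. Given an early pass, the ordinary HR and the arm success rates overstate the effect on average. At the design HR that means 0.21 against 0.415, and 41-45 points against 25 after a look-1 pass. The plan neither adjusts for this nor warns of it. At the final look the ordinary 95% interval does not match the 0.04 rule.

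Two stronger readings are tempting. One is that a look-1 pass requires an HR of 0.25 or less. That rests on 14 events, a planning count, and the limit is nearer 0.28-0.35 at 16-24 events. The other is that any early-pass estimate is certain to be exaggerated. That holds on average; a true HR well below the limit could be estimated without exaggeration.

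The figures assume proportional hazards, the SAP's event counts or the two accrual periods shown, and stopping at the boundary.

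**What to change.** In SAP 7.8 and 7.10.2.4, and Protocol 12.4.4:

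1. After an early pass, take the headline HR and arm success rates from all randomised mITT subjects once the last has 6 months of follow-up. Reconcile SAP 5.1 and 7.8 with Protocol 12.1 accordingly. Label interim-cut estimates as subject to early-stopping bias, and do not use them alone for pivotal planning.
2. At look 2 and the final look, report the stage-wise median-unbiased HR and 95% interval, matched to the boundaries, beside the ordinary Cox HR. First settle the look-2 boundary: Z = 2.611 corresponds to p = 0.0090, while SAP Table 2 gives 0.008.
3. At look 1, where stage-wise ordering changes nothing, report the boundary-matched repeated interval or a bias-adjusted HR.

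The cost is wording and a small calculation, with somewhat less favourable estimates and wider intervals. Item 1 reduces the bias without removing it, so the label is still needed.

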7.10.2.5. Datasets Analyzed

The mITT analysis set will be used for this objective.

7.10.2.6. Subgroup Analyses

Subgroup analyses are described in section 7.9.

7.10.3. Secondary: Single Procedure Chronic Treatment Success

The secondary objective characterizes the rate of chronic treatment success in Treatment and Control arms in the subgroup of subjects that do not undergo an additional pulmonary vein ablation procedure during the 90 day blanked follow-up period.

7.10.3.1. Hypothesis

There is no pre-specified hypothesis for this objective.

7.10.3.2. Performance Criteria and Rationale

There are no performance criteria for this objective.

7.10.3.3. Endpoint Definition

The endpoint for this objective is the primary effectiveness endpoint, chronic treatment success, as defined in section 7.10.2.3.

7.10.3.4. Analysis Methods

Kaplan-Meier curves will be used to estimate the rate of chronic treatment success for each study arm. Cox proportional hazards regression will be used to estimate the hazard ratio and its 95% confidence interval for the treatment effect between study arms. To support this analysis, a log-rank test will be used to determine if the freedom from chronic treatment failure rate differs between arms.

The Kaplan-Meier curves use the time that each subject is free from chronic treatment failure, defined from the date of procedure to the date of chronic treatment failure, if it occurs, or latest of the following: a) the last follow-up visit date, or b) the last date on which AF was assessed, if chronic treatment failure does not occur during the subject's study follow-up. Subjects will be included through all available study follow-up on or after the 6-month follow-up.

7.10.3.5. Datasets Analyzed

The secondary objective analysis set will be used for this objective.

7.10.3.6. Subgroup Analyses

Subgroup analyses are described in section 7.9.

7.10.4. Ancillary #1: Office systolic and diastolic blood pressure at 6 months compared to baseline

Compare the difference of office systolic and diastolic blood pressure at 6 months and baseline between study arms.

7.10.4.1. Hypothesis

There is no pre-specified hypothesis for this objective.

7.10.4.2. Performance Criteria and Rationale

There are no performance criteria for this objective.

7.10.4.3. Endpoint Definition

The endpoints for this objective are defined as:

- 1) The difference in office systolic blood pressure in a given subject between the 6-month follow-up measurement and the baseline measurement
 - a. For example: for subject 11111, the 6-month measure is 100 mm/Hg and the baseline measure is 80 mm/Hg so the endpoint value is 20 mm/Hg (100 minus 80).
 - b. For example: for subject 22222, the 6-month measure is 70 mm/Hg and the baseline measure is 100 mm/Hg so the endpoint value is -30 mm/Hg (70 minus 100).
- 2) The difference in office diastolic blood pressure in a given subject between the 6-month follow-up measurement and the baseline measurement.
 - a. Same logic as for systolic blood pressure.

